5.4 Population to be studied

Description and number:

This trial will recruit n = 120 healthy males and females aged between 18 - 55 years who are deemed eligible to participate as indicated by not meeting one or more of the exclusion criterion (see section below). For withdrawal of subjects see section 5.9.2.

Inclusion criteria:

Individuals with a body mass index greater than 18.5 kg/m², males and females aged between 18 - 55 years who are deemed eligible to participate as indicated by not meeting one or more of the exclusion criterion.

Exclusion criteria:

Participants will be excluded from participating within the project for the following reasons: Individuals with presence of psychiatric disorders, pathologic eating disorders, chronic diseases related to the metabolism of energy and nutrients (i.e. hyperthyroidism), difficulty in changing food habits, participants with special dietary needs (e.g. exclusion of whole food groups), and/or unable or unwilling to give informed consent. These exclusion criterion are set as they may influence an individual's ability to comply with the recommendations of the nutritional intervention.

Additional exclusion criterion includes: weight instable in the previous 3 months (evident by a loss or gain of more than 10% of total body weight), pregnant or potentially pregnant, post-menopausal, taking contraindicated medication (e.g. antibiotics, thyroid, hyperlipidemic, hypoglycemic, hypertensives, psychotropic drugs or appetite suppressants) or the use of any dietary supplement that might interfere with the results of the study. These additional exclusion criteria are set as they may exert an independent influence on microbiome and metabolic outcomes, anthropometric, biochemical, clinical, body composition (DEXA) analysis and/or dietary outcomes monitored throughout the intervention.

Sample size and statistical or power issues

Statistical power for a sample size of at least 120 participants to detect a medium effect size with 80% power was calculated upon previously published data on cross-over (Itsiopoulos et al. 2011 (n=27); Ryan et al. 2013 (n=12)) and single arm studies (Di Renzo et al. 2018 (n=188, split on FTO genotype); Jacka et al. 2017 (n=67); Papamiltiadous et al.

	
2016 (n=94); Parletta et al. 2007 (n=152)). In these studies, a 6 week to 3-month Mediterranean diet - control intervention was able to have a significant influence on a variety of physiological and psychological outcomes. Based on allowances for attrition, including predicted dropout rates, sample size was inflated by 20% for the current project (to n=120 overall), which takes a randomised cross over approach and accounts for genotypic influences on data outcomes.

5.5 Participant recruitment strategies and timeframes
	
Volunteers will be recruited from the RMIT University staff and student population, and also the local community (surrounding Melbourne Suburbs) by word of mouth and electronic (i.e. RMIT Facebook and Twitter) (Appendix F iii) and print advertisement (i.e. flyers) (Appendix F ii). Researcher contact details (phone and email) will be provided on electronic and print advertisement material.
 
Volunteers willing to participate in the study will be provided with a NHMRC 'Information to participants' form approved by RMIT HREC (Appendix B). This will be provided through email or mail based on volunteer preference. Volunteers will have the opportunity to receive further information over the telephone, email and/or face-to-face.
 
The principle research student [name], and Chief Investigator ([name]) will be the primary contacts for potential participants. Individuals expressing interest in participating in this study will be initially interviewed/screened over the phone or in person to determine suitability to participate in this study (please refer to section 5.4 for the inclusion and exclusion criteria). Participants believed to meet eligibility criteria will be invited to attend a familiarization session (section 5.6). (See Appendix F (iv) for an example of email correspondence).
 
Volunteers will be given time to think about participation (i.e. talk to family or friends) and they can consider participation during the time the study runs (i.e. there is no set timeframe). Volunteers willing to participate in the study will be asked to sign an Informed Consent form and reminded that participation is completely voluntary, and that they can withdraw from the study at any time.


5.6 Approach/es to provision of information to participants and/or consent
	
Participants will have the opportunity to be familiarised with the study purpose, design and the risks and benefits associated with the study. This is also an opportunity for participants to ask questions and to discuss the information. Participants will be asked to read and sign the informed consent document (if agreeing to participate).
 
It will be explained that participation is purely voluntary and that they can withdraw from the study at any time. How their privacy will be protected will also be discussed, along with the dissemination and publication of the project outcomes. Participants will be forewarned about potential genetic results (as per the National Statement guidelines on genetic data dissemination) (see Appendix D for an Ethical Defensible Plan).

	
Competence to give consent will be determined by an individuals ability to show that they understand the information. This will be determined by using a 'teach-back' method, where the researcher will prompt the individual to recall information provided. The determination of competence to give consent will be made by the Chief Investigator ([name]) and PhD student [name]. Participants will be informed of risks associated with the study via the Information to Participants Sheet (Appendix B).
 
No specific cultural group is either included or excluded in this project. Participant Information Sheets and Consent Forms will be provided in English as a default language. In circumstances where a participant does not speak English as their first language, assistance will be sought by RMIT University's "Languages, Translating and Interpreting" services to provide that participant with translated versions of these documents, specific to their first language.
 
There is no specific dependent or unequal relationship, however as investigators are staff of RMIT, and this study will be advertised and run at RMIT, it is possible that students of the investigators may volunteer to participate.
 
To ensure that participants' voluntary consent is not compromised by the relationship the following steps will be taken:
 
 1) Student volunteers willing to participate in this study will be provided with a RMIT HREC "Information to Participants" approved document and consent forms, which all other participants for this study will also receive. This will be provided through email or mail based on volunteer preference. 2) The participant will be reminded prior to commencement of the intervention that participation is completely voluntary and that they can withdraw from the study at any time. 
In the case of a potentially unequal or dependent relationship existing (i.e.: teacher/student), an investigator who does not have a relationship with the volunteering participant will be responsible for the procedures undertaken (i.e.: scheduling dates to attend sessions, taking biological samples etc).


5.7 Reimbursing of participants
	
Participants will be offered compensation in the form of a giftcard (to assist with grocery shopping and/or travel expenses) for the time committed to the project. A maximum of \$75 per person will be provided in installments. At the end of each of the three testing sessions, participants will receive a \$25 gift card. Participants will also be provided with a food hamper incorporating main items from the Mediterranean diet at the start of the Mediterranean intervention. This hamper will be valued at approximately \$50 per person.

5.8 Methodological Approach / Research Techniques
	

Buccal Swab/DNA Collection: Cells from inside of a person's cheek will be collected using a standard buccal swab. This is a relatively non-invasive way to collect DNA samples. Each swab will be used for genetic profiling using Single Nucleotide Polymorphism arrays as per manufactures instructions. Genetic data will be coded and re-identifiable. Participants will be advised that their material and data will not be released for use without their consent, unless required by law (as per the National Statement section 3.5).

Oral Glucose Tolerance Test (OGTT): Participant will ingest 1.75g of glucose per kilogram body weight (maximum 75g glucose) at each clinical session. Blood samples will be taken prior to, and at 30-mins, 60-mins and 120-mins following glucose ingestion. Insulin sensitivity will be calculated using the composite index (Matsuda & DeFronzo 1999) and homeostasis model assessment of insulin resistance calculated as per Matthews et al. (1985).

Body Composition Assessment: Body composition will be determined using a calibrated Lunar Prodigy Pro Dual-Energy X-ray Absorptiometry (DEXA) at each clinical session. The test involves having the subject lie down on their back in a standardised position. A low dose of radiation will then scan their entire body for approximately six minutes. The DEXA segments regions of the body (arms, trunk, and legs) into three compartments for determination of fat, muscle and bone composition.

Blood Samples: Details on how blood will be sampled, and the frequency, volume and treatment of samples are detailed in section 5.9. Serum will be assayed in the RMIT Biosciences Laboratory (Building 223) for a standard clinical chemistry profile (including glucose, triglycerides, cholesterol). Serum concentrations of inflammatory cytokines/chemokines and hormones (including ghrelin, insulin) will be determined using commercially available enzyme-linked immunoabsorbent assays in accordance with manufacturer's instructions.

Plasma metabolic profiling of metabolites associated with glucose, fat and protein metabolism will be performed using Gas Chromatography-Mass Spectrophotometry (GC-MS) as per methods described by Danaher et al. (2016). Plasma microRNA expression will be performed using microarray analysis and real-time-PCR.

Stool Samples: Stool samples will be collected by participants using a collection kit that includes a toilet hat (a specimen collector which hangs on the toilet seat), instructions for collecting/mailling the specimen, a collection tube, examination gloves, alcohol wipes, a postage-paid return mailing envelope, and biohazard mailing bag. Participants will be recommended to mail their samples to researchers immediately post collection. Samples can be stored at -80C prior to microbiome analysis.

Indirect Calorimetry: Expired air will be directed via a ventilometer into a mixing chamber and analysed for O₂ and CO₂ content. This involves participants wearing a respiratory mouthpiece and nose clip to have their respiratory gases measured in 30 sec intervals (for approximately 10 mins in total). Prior to each trial the gas analyser will be calibrated using commercially prepared gas mixtures. Respiratory data will be collected prior to the OGTT to determine resting metabolic rate. This data will be compared to calculations using Harris–Benedict equations, with adjustments for weight and physical activity levels applied, and used to inform nutritional (energy) requirements.

Dietary Intake and Quality Testing: Three-day weighed food records (2 weekdays and 1 weekend day) (Appendix I (i)) will be maintained in the week prior to the intervention, at the midpoint of the intervention, and during the week before the end of the intervention. Food records will provide information about baseline intake and adherence to the prescribed diet, and will be evaluated using a scientifically validated program (FoodWorks, Xyris Software) to determine macronutrient and micronutrient intake.

A validated online 120-item semi-quantitative food frequency questionnaire (Australian Eating Survey) (O'Brien et al. 2014) will be administered. Participants will self-report frequency of food

consumption for the previous 6 months at baseline and for the previous 8 weeks the post intervention clinical session. This questionnaire is not publicly available.

Adherence to the Mediterranean diet will be assessed using the Mediterranean Diet Adherence Screener Score (MEDAs) tool (Appendix H (iii)). method assigns a score of 0 or 1 according to the daily intake of nine components: high ratio of MUFA/SFA, moderate intake of alcohol, high intake of grains, vegetables, fruit and nuts, legumes and fish, low intake of meat and meat products, and moderate intake of milk and dairy products. The highest score of nine points reflects maximum adherence.

Diet quality will be assessed using the Healthy Eating Index via DIAL Software (Basiotis et al. 2002). The program gives different values between 0 and 100 considering the servings per day of food groups, macronutrients and selected micronutrients. The final value is classified into five categories (>80 points, “excellent diet”; ranging to 0 to 50 points, an “inadequate diet”).

Mood State will be assessed using two validated questionnaires, the Profile of Mood State (POMS) questionnaire and the Hospital Anxiety and Depression (HADS) questionnaire. The POMS questionnaire uses 65 words or statements that describe feelings people have, whereas the HADS questionnaire consists of 14 questions (7 items belonging to depression and 7 items belonging to anxiety categories) which are scaled (Appendix H (i) and H (ii)).

References:

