5.8.1 Participant Commitment	Approximately 16 weeks. This includes the two 8-week nutritional intervention periods (Mediterranean Diet and control diet).
5.8.2 Project Duration	The project will commence as soon as ethics has been approved, and the proposed project conclusion date is December 31 st , 2020.
5.8.3 Participant Follow up	Not applicable.
5.8.4 Discontinuation criteria	Participants may be discontinued from participating in the case that they enrol meeting inclusion criteria; however, their circumstances change to meet exclusion criterion during participation. For example, a participant requiring antibiotic medication during their participation will be discontinued as this medication can exert an independent influence on the gut microbiota.

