
5.14 Will participants in the study be requested to modify any other treatments or interventions they may be receiving?
 
NO
	

5.15 Will participants in the study be requested to modify their regular daily activities (e.g. dietary intake, sleep, exercise)?
 
YES
 
If YES, provide details:
 
The participants will be modifying their regular dietary intake as described in sections 4.3 and 5.3.
	

5.16 Are any medication(s)/treatment(s) not permitted before and/or during the trial?
 
YES
 
If YES, provide details:
 
Volunteers taking contraindicated prescription medication (e.g. antibiotics, thyroid, hyperlipidemic, hypoglycemic, hypertensives, psychotropic drugs or appetite suppressants) will be excluded from participating (or have their participation discontinued) as these medications may exert an independent influence on microbiome, metabolic, anthropometric, biochemical, clinical and/or dietary outcomes monitored throughout the intervention.
	

5.17 Procedures for monitoring compliance
	
Participants will receive weekly support-orientated phone calls to ensure that procedures are being followed and how they are tolerating the intervention.
 
To monitor compliance to the dietary protocol, validated questionnaires will be used as described in section 5.8.

5.18 Are there any likely or expected negative side-effects of the intervention?
 
NO
	

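### The antibiotic exclusion covers current use only, so a course completed shortly before the single baseline stool sample is admitted and may bias the comparison with habitual diet

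*Protocol*

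**What the plan says.** Entry: section 5.4 of the protocol excludes anyone "taking contraindicated medication (e.g. antibiotics, thyroid, hyperlipidemic, hypoglycemic, hypertensives, psychotropic drugs or appetite suppressants". The same sentence excludes "the use of any dietary supplement that might interfere with the results of the study". Neither item carries a period before enrolment. The sentence does set one for body weight: "weight instable in the previous 3 months (evident by a loss or gain of more than 10% of total body weight".

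Permitted medication: the question heading section 5.16 is "Are any medication(s)/treatment(s) not permitted before and/or during the trial". The answer is yes, but the detail again begins "Volunteers taking contraindicated prescription medication" and gives no interval before the trial. It does not mention supplements.

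After entry: section 5.8.4 states that "a participant requiring antibiotic medication during their participation will be discontinued as this medication can exert an independent influence on the gut microbiota".

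Use of the baseline: gut bacteria diversity and composition is a primary outcome (sections 4.8 and 5.13). Aim (i) in section 4.7 compares the Mediterranean diet with the participant's habitual diet, represented by the baseline results, and with the control diet. Section 5.9.1 provides one baseline stool sample, taken within a week of the baseline session, and one sample at the end of each diet. Section 5.11 tests main effects of time and genotype-by-time interactions.

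**The concern.** The protocol gives a reason for keeping antibiotic users out: the drugs can change gut bacteria independently of diet. It applies that reason to a course taken during participation, even one finished weeks before the next stool sample. It does not apply it to a course finished shortly before the first sample, and it does not explain the difference.

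If a recently completed course has left the gut bacteria altered at baseline, the participant drifts back towards normal during the first diet, whichever diet that is. A before-after comparison cannot tell this drift from an effect of diet. Because there is only one baseline sample, nothing in the data would reveal it. A later analysis plan cannot exclude people already enrolled, and no item shown in the protocol guarantees that past antibiotic use is recorded.

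**Working it through.** **Step 1: the rules side by side.**
- Antibiotics before entry (5.4, 5.16): present use only, no interval.
- Supplements before entry (5.4 only): use that might interfere, no interval and no list.
- Weight before entry (5.4): 3-month look-back.
- Antibiotics after entry (5.8.4): any need for them ends participation, with gut bacteria given as the reason.

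No section covers a course completed before entry, so the written criteria admit it. The protocol states no figure to reproduce here.

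**Step 2: which comparisons are exposed.** Let f be the share of participants with a recent course and d their mean recovery, in SD units of the outcome, by week 8.
- Each diet against baseline: every change from baseline contains the recovery, so the mean change shifts by f x d with no diet effect at all. The main effect of time in section 5.11 contains the same shift.
- Mediterranean against control: recovery belongs to the period, not the diet. Randomised order spreads it over both diets on average. If recovery is complete by week 8, the two post-diet samples do not differ on account of it.
- Between genotype groups: genotype is not randomised, but nothing in the documents links it to recent antibiotic use. The imbalance is therefore due to chance and has mean zero.

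**Step 3: size of the shift, under assumptions.** The documents give neither f nor d. Assume f = 0.05 to 0.15 (6 to 18 of the planned 120) and d = 0.5 to 1.5 SD.
- Low: 0.05 x 0.5 = 0.025 SD
- Middle: 0.10 x 1.0 = 0.10 SD
- High: 0.15 x 1.5 = 0.225 SD

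**Step 4: genotype groups.** Assume two groups of 20 and a change SD of 1 (neither is in the documents).
- SE of the difference in change without recent users: sqrt(2/20) = 0.316.
- SD added by chance imbalance: d x sqrt(2f(1-f)/20). Middle values: 1 x sqrt(2 x 0.10 x 0.90/20) = 0.095. High values: 1.5 x sqrt(2 x 0.15 x 0.85/20) = 0.169.
- Combined SE, middle: sqrt(0.316² + 0.095²) = 0.330, about 4% larger. High: sqrt(0.316² + 0.169²) = 0.359, about 13% larger.

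This is a modest loss of precision, not a systematic genotype effect.

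**Step 5: room for deferral.** Section 5.8.2 sets the project's conclusion at 31 December 2020, and participation lasts 16 weeks (112 days). The last workable baseline is therefore about 10 September 2020. If the interval were, for illustration, 3 months, a volunteer just off a course and screened after about 10 June 2020 could not be deferred and would be lost.

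**The case against.** The best defence is that the gap is narrow. Volunteers are screened against section 5.4 and then invited to a familiarisation session before baseline. Someone who finishes a course the day before baseline would often still be taking it at screening, and so be excluded. If participation begins at consent, section 5.8.4 may also reach a course started between consent and baseline. A medical questionnaire is completed at the clinical session, and its content (Appendix C) is not shown.

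This makes the day-before case an extreme one but does not close the gap. No interval from screening to baseline and no re-check of medication is stated, and a course finished before screening is not caught at all. Even if the questionnaire asks about recent use, the written criteria would not exclude on the answer.

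Several objections do stand. The documents say that antibiotics can influence gut bacteria, but not for how long after stopping, so the baseline may be disturbed; it is not shown to be. The supplement criterion speaks of use rather than of taking, and can be read to cover recent use that might interfere, so it should not be described as limited to current use. The control diet comparison in aim (i) would show recovery common to both diets. The time that section 5.5 allows for considering participation lies within the running of the study, so deferral is not free.

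**Conclusion.** The point holds as an inconsistency in eligibility. The protocol's reason for removing antibiotic users after entry applies equally to a course completed shortly before baseline, and the stated criteria admit that course. What is exposed is the comparison with habitual diet in aim (i) and the main effect of time for the gut-bacteria outcome. The shift is about 0.03 to 0.23 SD, and 0.10 SD at middle values. It rests wholly on the assumed 5-15% recent use and 0.5-1.5 SD recovery, and the upper figure needs both extremes at once.

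A reader might infer two stronger conclusions. One is that the Mediterranean-versus-control result is biased; randomised order largely protects it. The other is that clustering of recent users could create a false genotype response; chance clustering has mean zero and enters the variance that the test already uses. The documents support neither. Nor do they support 3 months as the right interval for antibiotics, since that window is given for weight alone.

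**What to change.** In sections 5.4 and 5.16, extend the antibiotic exclusion from current use to use within a stated interval before the baseline stool sample. The investigators should choose and justify the length. The 3-month weight window is one candidate, but the documents offer no justification for it here. In section 5.4, make clear that supplement use includes recent use over the same interval.

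Reconcile both sections with section 5.8.4, and state when participation begins, so that a course falling between screening and baseline comes under one defined rule. Check recent use at screening and again on the baseline medical questionnaire. Volunteers inside the interval can be re-screened once it has passed.

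The cost is protocol wording and one questionnaire item. A small share of volunteers would start later, and those screened too close to the December 2020 end date would be lost. The change must be made before baseline samples are taken, because a disturbed baseline cannot be repaired afterwards.
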